- Formulation: Matching placebo will be supplied as an identical formulation to the active formulation without dupilumab, in a prefilled syringe to deliver placebo in a 2 mL injection.
- Route of administration: SC injection.
- Dose regimen: Q2W after an initial loading dose (2 injections) on Day 1.

[figure not shown]
Posttrial access to study medication: Posttrial access to study medication will be assessed in accordance to the country requirements and the legislation in place.

Statistical considerations:

- **Sample size calculations and preservation of Type I error for the two primary endpoints**

To control the type-I error rate for the 2 primary endpoints, a hierarchical testing procedure will be applied at a 2-sided 5% significance level, ie, each hypothesis will be formally tested only if the preceding one is significant at 5% level. The hierarchy of the tests for primary endpoints will be:

- a) Proportion of participants achieving response of FeNO <25 ppb at Week 24
- b) Percentage change from baseline to Week 24 in untrimmed distal [s]iVaw at TLC

- **Primary analysis:**

For the primary endpoint proportion of participants achieving FeNO <25 ppb at Week 24, the analysis will be conducted by Cochran-Mantel-Haenszel (CMH) test adjusted by stratification factors. Comparison of the proportions of responders between dupilumab and placebo will be derived, and corresponding odds ratios and 95% CI along with the p-value will be reported. For participants who discontinued the study treatment, off-treatment data will be used to determine the responder/non-responder status. Missing data at Week 24 will be considered as non-responders.

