9.4.1 Efficacy analyses

All efficacy analyses will be performed on the Intent-to-treat (ITT) population, unless otherwise noted.

Note that at each scan, images will be taken from each zone of the lung, thus there will be multiple observations per visit for each imaging parameter. Data may be logarithmically transformed prior to analysis if extreme skewness was observed based on blinded data review.

Table 7 - Efficacy analyses

Endpoint	Statistical Analysis Methods
Primary	

 Proportion of participants achieving FeNO <25 ppb at Week 24 	
 The primary analysis will be conducted by Cochran-Mantel-Haenszel (CMH) test adjusted by stratification factors. Comparison of the proportions of responders between dupilumab and placebo will be derived, and corresponding odds ratios and 95% CI along with the p-value will be reported. For participants who discontinued the study treatment not due to COVID-19 pandemic, off-treatment data will be used to determine the responder/non-responder status. For any participants discontinue the study treatment due to COVID-19 pandemic, off-treatment data will be set to missing. Missing data at Week 24 will be considered as non-responders.

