Primary objective: To assess the effect of dupilumab on lung inflammation and related changes in airway volumes detectable by functional respiratory imaging.					
Primary endpoints	Proportion of participants achieving FeNO <25 ppb at Week 24	ITT	
 Discontinuation of study intervention due to Covid-19 pandemic^a (IcEv1), off-study intervention data will be set as missing (hypothetical strategy). Discontinuation of study intervention not due to Covid-19 pandemic (IcEv2), all data collected following schedule after the study intervention discontinuation will be used in the analysis (treatment policy strategy). 		
Achievement of FeNO <25 ppb at Week 24 will be analyzed using a Cochran-Mantel-Haenszel (CMH) test adjusted by stratification factors (region and ICS dose level). Corresponding odds ratios and 95% CI with p-value will be reported.
 
Missing data at Week 24 will be considered as non-responders.

Secondary objective: To evaluate the effect of dupilumab at Week 24 on bronchodynamics, hyperinflation, airway resistance, airway wall volume, ventilation defects and mucus plugging derived from high-resolution computed tomography (HRCT) scans, patient-reported outcomes, FeNO and spirometry.					
Percent change from baseline to Week 24 in untrimmed distal specific airway volume ([s]iVaw) at total lung capacity (TLC)	ITT	
 Discontinuation of study intervention due to Covid-19 pandemic^a (IcEv1), off-study intervention data will be set as missing (hypothetical strategy). Discontinuation of study intervention not due to Covid-19 pandemic (IcEv2), all data collected following schedule after the study intervention discontinuation will be used in the analysis (treatment policy strategy). 		
A mixed effect model for repeated measures (MMRM) under the missing at random (MAR) framework will be used. The MMRM will use percent change from baseline in untrimmed distal [s]iVaw at TLC up to Week 24 as the response variable, and will include study intervention, baseline value, region, ICS dose level, visits, study intervention by visit interaction, and baseline by visit interaction terms all as fixed effects.
 
Region, ICS, study intervention and visits will be considered as categorical parameters. No explicit imputation will be done for missing data. Baseline values corresponding to the outcome variables should be used.
	

Endpoint Category (estimand)	Estimands			

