6.2.4. Biomarkers at baseline

The following biomarkers (see [Section 15.12](#)) will be summarized at baseline:

- FeNO (ppb)
- FeNO in class (<25, ≥25 to <50, ≥50 ppb)
- Blood Eosinophil count (cells/µL)
- Eosinophils counts in class (≥300 to <500, ≥500 cells/µL)

Blood Eosinophils counts collected in $10^9/L$ will be converted to cells/µL using the following formula:

$$1 \ 10^9/L * 1000 = \text{cells}/\mu\text{L}$$

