8.1.1. Primary analysis

Proportion of participants achieving FeNO <25 ppb at week 24 will be analyzed with a Cochran-Mantel-Haenszel (CMH) test adjusted by stratification factors (ICS dose level at baseline and region). Comparison of the proportions of responders between dupilumab and placebo will be derived, and corresponding odds ratios and 95% CI along with the p-value will be reported.

For participants who discontinued the study treatment not due to COVID-19 pandemic, off-treatment data will be used to determine the responder/non-responder status. For any participants who discontinued the study treatment due to COVID-19 pandemic, off-treatment data will be set to missing. Missing data at week 24 will be considered as non-responders.

Percent change from baseline in untrimmed distal [s]iVaw at TLC will be analyzed with a MMRM model under the MAR framework. The MMRM model will use percent change from baseline in untrimmed distal [s]iVaw up to week 24 as response variable and include study intervention (dupilumab, placebo), baseline value of untrimmed distal [s]iVaw at TLC, region (EE/ROW), ICS dose level (medium/high), visits (up to week 24), study intervention by visit interaction, and baseline untrimmed distal [s]iVaw at TLC by visit interaction terms all as fixed effects. An unstructured correlation matrix will be used to model the within-participant errors.

The Kenward-Roger approximation (ddfm=kr) will be used to estimate the denominator of degrees of freedom. Parameters will be estimated using restricted maximum likelihood method with the Newton-Raphson algorithm. The adjusted LS mean in percent change from baseline of each study intervention group, the LS mean difference between the dupilumab and placebo groups, and the corresponding SEs and 95% CIs will be provided at all scheduled visits. The p-value corresponding to the LS mean difference will be provided at Week 24 only.

For participants who discontinued the study intervention before Week 24 not due to the COVID-19 pandemic, off-study intervention imaging data measured up to Week 24 will be included in the analysis. In contrast, for any participants discontinuing the study intervention due to the COVID-19 pandemic, off-study intervention data will not be included (ie, set to missing) but will be assumed missing at random.

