8.1.5. Sensitivity analysis

A sensitivity analysis on the two primary endpoints of achievement of FeNO <25 ppb at Week 24 and percent change from baseline to week 24 in untrimmed distal [s]iVaw at TLC will be carried out. For the latter, an analysis of covariance model (ANCOVA) with data from multiple imputation (MI) on missing results under an assumption of missing at random (MAR) will be used. For response of FeNO <25 ppb at week 24, a CMH testing procedure with data from multiple imputation (MI) on missing results under an assumption of missing at random (MAR) will be performed. Under this assumption, each missing score will be imputed 100 times and incorporated with non-missing data from 100 complete datasets. Each dataset will include FeNO / untrimmed distal [s]iVaw at baseline, week 4, week 12 (only for FeNO), and week 24, as well as relevant covariates specified below to support the analysis. Following steps will be conducted for this analysis. The number of imputations (100) will be informally verified by replicating sets of 100 imputations and checking whether the combined results are stable. If not stable, the number of imputations will be increased and informally checked as above, until stable estimates are obtained.

- Use the Markov chain Monte Carlo (MCMC) method to impute for intermittent missing values by study intervention group and to create 100 datasets with monotone missing pattern. According to the nature of the endpoint, minimum and maximum values will be specified in this imputation.
- For each of 100 datasets with monotone missing pattern created from MCMC imputation, use monotone regression method to impute remaining missing value by study intervention group up to week 24. In the imputation regression model, the following covariates will be included:
 - region (EE/ROW) and ICS dose level (medium/high)Percent change from baseline at week 24 and achievement of FeNO <25 ppb can be calculated with non-missing score or imputed score for every single participant in all datasets. All 100 datasets with full imputation for missing values will be input to the following models.

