- Repeatedly perform ANCOVA modeling for each of 100 datasets with full imputation for missing values. Percent change from baseline of untrimmed distal [s]iVaw at TLC at week 24 will be analyzed on the ITT population in this ANCOVA model, and study intervention (Dupilumab, Placebo), baseline of the analyzed endpoint and respective above covariates, will be included as covariates.
- The adjusted LS means in change or percent change from baseline of each study intervention group, the LS mean difference between the dupilumab and placebo groups, and the corresponding SEs and 95% CIs of the differences generated from the 100 ANCOVA models will be combined using Rubin's formula and presented in a statistical table for the ITT population.

- Repeatedly perform CMH testing on each of 100 datasets with full imputation for missing values. Achievement of response of FeNO <25 ppb at week 24 will be analyzed on the ITT population, adjusted on stratification factors.
- The Wilson-Hilferty transformation will be used to perform a combined CMH test and odds-ratios will be combined using a log transformation and Rubin's formula. The combined p-value, odds-ratio and corresponding CIs will be presented in a statistical table for the ITT population.

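### Cheap improvement, not an error: the FeNO <25 ppb test that gates every other confirmatory claim leaves out baseline FeNO; the SAP's own 50 ppb cut could be added as a CMH stratum

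*SAP*

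**What the plan says.** SAP 8.1.1 specifies a "Cochran-Mantel-Haenszel (CMH) test adjusted by stratification factors (ICS dose level at baseline and region". The same adjustment set appears wherever the test is stated:

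- SAP Table 2-2: "Achievement of FeNO <25 ppb at Week 24 will be analyzed using a Cochran-Mantel-Haenszel (CMH) test adjusted by stratification factors".
- Protocol Table 7: "The primary analysis will be conducted by Cochran-Mantel-Haenszel (CMH) test adjusted by stratification factors".
- Protocol synopsis: "the analysis will be conducted by Cochran-Mantel-Haenszel (CMH) test adjusted by stratification factors".
- Multiple-imputation version, SAP 8.1.5: "Achievement of response of FeNO <25 ppb at week 24 will be analyzed on the ITT population, adjusted on stratification factors".

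The other analyses treat baseline differently. The [s]iVaw model (SAP 8.1.1) and the model for continuous FeNO change (SAP 8.2.2, by way of 8.2.1) each adjust for the baseline of the variable analysed.

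Baseline FeNO is available. It enters the imputation datasets: "Each dataset will include FeNO / untrimmed distal [s]iVaw at baseline, week 4, week 12 (only for FeNO), and week 24". It is tabulated at baseline as "FeNO in class (<25, ≥25 to <50, ≥50 ppb" (SAP 6.2.4), and the 50 ppb cut defines a subgroup of the primary analysis (SAP 8.1.4). None of these uses changes the primary p-value.

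**The concern.** Entry requires FeNO of at least 25 ppb, rechecked at the randomization visit (Protocol 5.1, I 06), and response is a value below 25 ppb. Participants therefore start at different distances from the same line. If one arm happens to hold more participants with high baseline values, the planned test has no way to allow for it.

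This matters because the test is a gate. Under SAP 4.1 and 8.2.5, failure stops formal testing of [s]iVaw (itself at about 64% power, Protocol 9.2), mucus score and [s]iRaw.

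**Working it through.** **Inputs from the documents.** 2:1 allocation; 87 evaluable (58 and 29); 10% dropout; two-sided 5%; missing Week 24 FeNO counted as non-response; strata of ICS dose by region; at most 40% Eastern Europe.

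**The plan's own figures.** 87 / (1 − 0.10) = 96.7, rounded up to 97, which reproduces. The 64% for [s]iVaw cannot be recomputed because effect and SD are redacted; at 58 vs 29 it implies a standardized difference of about 0.53. FeNO response rates and FeNO power are redacted, and no baseline-to-Week 24 correlation is given.

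**Step 1: is baseline prognostic?** From x ppb, response needs a fall of more than (x − 25)/x. That threshold is below 50% for x under 50 ppb and at least 50% from 50 ppb upward. Baseline is very likely prognostic; how strongly is unknown.

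**Step 2: chance imbalance.** With about 65 vs 32 participants and a share p below 50 ppb, the between-arm difference has SD = √[p(1 − p)(1/65 + 1/32)]. Assumed p = 0.33 gives 0.102 and p = 0.57 gives 0.107. The chance of 10 points or more in one direction is then 16% and 18% (simulated: 14.5–18.5%).

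**Step 3: simulation.** Assumptions: N = 97; permuted blocks of 6 within four strata; 40% Eastern Europe; 50% high ICS; bivariate normal ln FeNO with baseline truncated at 25 ppb; two baseline distributions (median 38 ppb, log SD 0.6; median 60 ppb, log SD 0.7, before truncation); 10% missing set to non-response. Response of 15% vs 40% after that rule is 15/0.9 = 16.7% vs 40/0.9 = 44.4% in evaluable participants. Each cell shows planned 4-stratum CMH → 8-stratum CMH with baseline <50 / ≥50 ppb.

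| Correlation after truncation | Average power | Imbalance ≥10 points against dupilumab | Imbalance ≥10 points in its favour |
|---|---|---|---|
| 0 | 73–74% → 71–72% | not run | not run |
| about 0.2 | 74% → 72% | not run | not run |
| 0.35–0.39 | 74% → 74% | 61–64% → 72–73% | 82% → 73% |
| 0.59–0.64 | 74% → 77–78% | 52–59% → 77–78% | 87–89% → 75–77% |
| 0.77–0.80 | 74% → 81–83% | 46–54% → 82–83% | 90–94% → 79–83% |

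Repeat runs agreed within simulation error. They reached 84% at the top of the average column, 45% at the bottom of the adverse column, and 71% at the bottom of the favourable column after adjustment.

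Larger effects leave less room. Average power at 15% vs 44% is 85% → 85–92%, and at 15% vs 49% it is 94% → 94–98%. At 15% vs 55% it is 98.3–98.4% → 98.0–99.4%, and at 15% vs 60% it is 99.5–99.6% → 99.4–99.9%.

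**Step 4: a different response model.** Response was set directly by baseline class: placebo 35% / 10% and dupilumab 65% / 30% (below / at or above 50 ppb), with half the participants in each class.

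- Average power goes from 68% to 71%.
- With at least 15 points of imbalance against dupilumab (8% of trials) it goes from 47% to 69%; in its favour (8%), from 89% to 68%.
- The correlation of the CMH numerator with the imbalance goes from −0.32 to +0.03.
- With baseline weakly prognostic, power falls from 71% to 69%; with baseline not prognostic, from 77% to 75%.
- With a large effect, power goes from 99.1% to 99.3%.

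**Step 5: size and sparsity.** With 15% response in both arms, type I error is 4.5–5.0% planned and 4.6–4.9% with eight strata; at 5%, 10% or 30% in both arms, eight strata give 3.8–5.2%. Participants in strata holding only one arm, who drop out of the test, are 0.6–1.1% at 40% Eastern Europe and about 2–3% at 10–20%.

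**The case against.** The planned test is conventional, matches the randomization strata and holds its level, so a further prognostic stratum could be called a matter of preference. The largest differences apply only to the roughly one trial in six with adverse imbalance; about as many trials lose power when imbalance runs the other way. FeNO power is redacted. The amendment summary ties the smaller sample to the switch to FeNO, and Protocol 9.2 accepts 64% for [s]iVaw at that size. It is therefore reasonable to infer, though it cannot be read, that the FeNO test was well powered. The subgroup results by 50 ppb and the baseline table will at least make an imbalance visible. The change also needs a protocol amendment.

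Much of this stands. It limits the average gain and rules out calling the plan defective. It does not remove the reason to act: a descriptive subgroup cannot alter the gate, and the plan already adjusts continuous FeNO and [s]iVaw for baseline.

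A reader might infer that the planned test is biased, or that the gate is underpowered. The documents support neither. Unconditional type I error is about 5%, and the 74% power at 15% vs 40% is a property of assumed rates. Nor does adjustment always help: it costs about 2 points on average if baseline turns out weakly or not prognostic.

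**Conclusion.** A worthwhile, inexpensive improvement to a valid analysis. Its main benefit is that the gate nearly stops depending on how baseline FeNO happens to fall between arms. The average power effect, from about −2 to about +10 points, is secondary. It shrinks to about 1 point at most when gate power is already about 98% or more.

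Confidence is medium. That baseline FeNO is omitted, and that the gate has the role described, is plain from the text. The size depends on assumed response rates, baseline distributions and correlations.

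**What to change.** Before database lock and unblinding:

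- Add baseline FeNO <50 / ≥50 ppb as a third CMH stratification factor for the primary p-value and odds ratio. Use the baseline definition in SAP 4.4.6, and place any value below 25 ppb in the <50 class, since the SAP 8.1.4 split does not cover it.
- Carry the same factor into the multiple-imputation analysis. SAP 8.1.5 already says "The Wilson-Hilferty transformation will be used to perform a combined CMH test", and its datasets already hold baseline FeNO.
- Keep the two-factor CMH as a sensitivity analysis.
- State that strata holding only one arm contribute nothing to the test.
- Align SAP 8.1.1, Table 2-2 and 8.1.5 with Protocol Table 7 and the synopsis.

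No more elaborate model-based test is needed.

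**Cost.** No new data. The SAP needs a version after Final 2.0, which its Introduction allows before lock, and the protocol wording must go through the amendment rules in Protocol 10.1.1. The odds ratio becomes conditional on baseline FeNO as well as on ICS dose and region. The sponsor also accepts the power given up under favourable imbalance, the possible average loss of about 2 points, and the small share of participants in one-arm strata.
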